9.5. Pregnancies

For any subjects in the Safety population who became pregnant during the study, every attempt will be made to follow these subjects to completion of pregnancy to document the outcome, including information regarding any complications with pregnancy and/or delivery.

Listing 18, Listing 19, Listing 20, Listing 21, and Listing 22 will present any study pregnancies and their outcomes.

9.6. Clinical Laboratory Evaluations

Clinical laboratory parameters to be evaluated at the Screening Visit (Visit 00) and on Day 08 (Visit 02) will include a White Blood Cell Count (WC), HGB, HCT (only at Visit 00), Platelet Count, ALT, AST, Serum Creatinine, Ferritin (at Visit 00), Prothrombin Time (PT) and Activated Partial Thromboplastin Time (aPTT). The grading scales for clinical laboratory evaluations are presented in Table 11 and Table 10. Clinical laboratory evaluations assessed on Day 1 prior to the first study vaccination will be considered as baseline.

Subjects with HGB below the lower limit of normal (LLN) at Day 8, or subjects who experience a drop of ≥ 0.5 g/dL between screening and Day 8, will have HGB re-drawn at Day 22. If HGB remains low (result is less than LLN or ≥ 0.5 g/dL lower than screening levels) at Day 22, or if HGB is not collected at Day 22, hemoglobin labs will be re-drawn at Day 57. Any subject where HGB results remain low at Day 57 will have no further PBMC collected. HGB and Ferritin will be drawn for all subjects at Day 113 (approximately 22 days post QIV vaccination). Ferritin results taken at Day 57 will be used for clinical decision making only – values will not be graded or included in summaries of clinical laboratory data, but will be included in the listings of hematology results (Listing 15).

The distribution of laboratory results by severity, study day and treatment group will be presented beginning with [Table 54](#), and continuing through [Table 65](#). Descriptive statistics including mean, standard deviation, median, minimum and maximum values and change from baseline by study day will be summarized for each parameter in [Table 59](#) and [Table 67](#). Box plots illustrating the change from baseline for each laboratory parameter will be presented in [Figure 56](#), [Figure 57](#), [Figure 58](#), [Figure 59](#), [Figure 60](#), [Figure 61](#), [Figure 62](#), and [Figure 63](#). Subject visits with abnormal laboratory results, Grade 1 severity or higher, will be presented in [Table 52](#) and [Table 53](#) for chemistry and hematology parameters, respectively. Abnormal results will be summarized by visit and study arm in [Table 58](#) and [Table 66](#) for chemistry and hematology parameters, respectively.

A complete listing of individual clinical laboratory results will be presented in [Listing 14](#) and [Listing 15](#) for chemistry and hematology, respectively, sorted by subject ID, parameter, and visit number.

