## 9. ASSESSMENT OF SAFETY

### 9.1 Specification of Safety Parameters

Safety will be assessed by the frequency and severity of:

1. SAEs occurring from the time of the first study vaccination through 12 months after the first vaccination.
2. AESIs (wheezing, otitis media) and NOCMCs occurring from the time of the first study vaccination through 3 months after the first vaccination.
3. Solicited Adverse Events – reactogenicity events occurring from the time of experimental (first) study vaccination through 7 days after the first study vaccination. See tables listed in [section 9.2.2 and 9.2.6](#) for local upper respiratory, respiratory tract assessment, and systemic symptoms:
4. Unsolicited Non-Serious Adverse Events –non-serious AEs occurring from the time of the first study vaccination through approximately 21 days after the first study vaccination.
5. Clinical safety laboratory AEs occurring at approximately 7 days after the first vaccination. Parameters to be evaluated include a WBC, HGB, Platelet Count, ALT, AST, Serum Creatinine, Ferritin level, PT and aPTT. HGB will also be repeated at Day 22 if there is a drop in HGB level from screen to Day 8 of  $\geq 0.5$  g/dL or results are  $<$  lower limits of normal. If unable to collect at Day 22, collect at Day 57. If drawn at Day 22 and the results are still low, repeat at Day 57. If HGB results are still low at Day 57, no further PBMC collection will be done. HGB and Ferritin level will be drawn at Day 113. If the ferritin is  $< 15$  ng/mL and/or the HGB is less than the lower limits of normal, will recommend follow-up with primary care provider for consideration of multivitamins with iron.

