12. SUMMARY OF CHANGES IN THE CONDUCT OF THE STUDY OR PLANNED ANALYSES

Enrollment into Protocol 17-0012 was paused in November 2018 for safety concerns and revision as follow:

- Subjects enrolled beyond early November would receive the protocol-provided QIV at an unacceptably late time in the 2018-2019 influenza season.
- Consistent drops in HGB post first vaccination had been noted among the subjects enrolled in 2018.

As a result, the protocol was updated to include additional blood draws past Visit 02 to confirm that low HGB values return to normal, or to implement a clinical plan for subjects who do not return to normal (see Section 9.6 for further details). Enrollment is to resume in 2019 to enroll the remaining 31 subjects, which will allow sufficient time to receive the QIV vaccination prior to the 2019-2020 influenza season. An interim analysis of the subjects enrolled in 2019 was added to the protocol at this time.

The plan to pursue exploratory anti-NA antibody assays was changed from being depending on observing increased sIgA response to the M2SR H3N2 strain in the M2SR vaccinated group, to being contingent on observing increased HAI or MN seroconversion or 4-fold rise rates in the M2SR vaccinated group compared to placebo post M2SR vaccination (see Section 8.3).

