Eye Pruritus	Transient of intermittent or minimal interference and no intervention	Persistent or frequent episodes, some interference with daily activity	Significant symptoms, prevents daily activity, or seeks medical attention
Eye Redness (Conjunctivitis)	Asymptomatic eye redness	Symptomatic eye redness, some interference with daily activity	Eye redness prevents daily activity or seeks medical encounter
Allergy	Pruritus with or without rash, no medical intervention	Localized urticaria, with intervention	Generalized Urticaria, Anaphylaxis, or Angioedema
Quantitative Systemic Reactions			
Fever* - oral ^{#†}	38.0°C – 38.4°C 100.4°F – 101.1°F	38.5°C – 38.9°C 101.2°F – 102.0°F	>38.9°C >102.0°F

# Oral temperature assessed on Day 1 prior to the first study vaccination will be considered as baseline.
 
* A fever can be considered not related to the study product if an alternative etiology can be documented.
 
† Subjects must not eat or drink anything hot or cold, or smoke within 10 minutes prior to taking oral temperature.
			

Table 8: Respiratory Tract Assessment Grading Scale: Erythema and Induration

Parameter	Grade 1	Grade 2	Grade 3
Erythema (Redness)	Very slight or barely perceptible redness	Well defined redness	Moderate to severe beet redness to eschar
Induration (Swelling or edema)	Very slight or barely perceptible swelling	Slight swelling (edges of area well-defined by definite raising)	Moderate swelling (edges raised approximately 1 mm)

Table 9: Otitis Media and Wheezing Grading Scale

Symptom	Mild (Grade 1)	Moderate (Grade 2)	Severe (Grade 3)
Otitis Media	No interference with daily activity	Some interference with daily activity	Significant interference, prevents daily activity
Wheezing	No interference with daily activity	Some interference with daily activity	Significant interference, prevents daily activity

12.4.1 Individual Laboratory Measurements and Abnormal Laboratory Values**Table 10: Laboratory Adverse Event Grading Scale (Hematology)**

Hematology Parameter	Mild (Grade 1)	Moderate (Grade 2)	Severe (Grade 3)
WBC cells/mm ³ ; 10 ³ cells/ μ L (Decrease)	2.0 – 2.4	1.50 – 1.0	<1.5
HgB g/dL 9-12 years of age	9.5-10.4	8.5-9.4	<8.5
HgB g/dL Males \geq 13 years of age	10.0 – 10.9	9.0 - < 10.0	< 9.0
HgB g/dL Females \geq 13 years of age	9.5 – 10.4	8.5 - < 9.5	< 8.5
Platelets cell/mm ³ /UL	100- < 125	50- < 100	< 50
PT	1.1 - <1.25 x ULN	1.25 - < 1.50 x ULN	\geq 1.50 x ULN
aPTT	1.1 - < 1.66 x ULN	1.66 - <2.33 x ULN	\geq 2.33 x ULN

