14.3.5.2 Hematology Results

Table 60: Laboratory Results by Parameter, Maximum Severity, Time Point, and Study Group – Any Hematology Parameter, Safety Population

Time Point	Study Group	N	None		Mild / Grade 1		Moderate/ Grade 2		Severe/ Grade 3		Missing		Not Applicable	
			n	%	n	%	n	%	n	%	n	%	n	%
Screening	M2SR	x	x	xx	x	xx	x	xx	x	xx	x	xx	NA	NA
	Placebo	x	x	xx	x	xx	x	xx	x	xx	x	xx	NA	NA
Day 8	M2SR	x	x	xx	x	xx	x	xx	x	xx	x	xx	NA	NA
	Placebo	x	x	xx	x	xx	x	xx	x	xx	x	xx	NA	NA
Day 22 ^a	M2SR	x	x	xx	x	xx	x	xx	x	xx	x	xx	x	x
	Placebo	x	x	xx	x	xx	x	xx	x	xx	x	xx	x	x
Day 57 ^b	M2SR	x	x	xx	x	xx	x	xx	x	xx	x	xx	x	x
	Placebo	x	x	xx	x	xx	x	xx	x	xx	x	xx	x	x
Max Severity Post Baseline	M2SR	x	x	xx	x	xx	x	xx	x	xx	x	xx	NA	NA
	Placebo	x	x	xx	x	xx	x	xx	x	xx	x	xx	NA	NA

Note: The “Max Post Baseline” rows indicate the maximum severity experienced by each subject at any time point post baseline, including unscheduled assessments.

N = Number of subjects in the Safety Population

^a Any subject with either a drop of > 0.5 g/dL or results less than the lower limit of normal (based on age and gender) at Day 8 will have hemoglobin only re-drawn at Day 22

^b Any subject with either a drop of > 0.5 g/dL or results less than the lower limit of normal (based on age and gender) at Day 22 will have hemoglobin only re-drawn at Day 57

Table 61: Laboratory Results by Parameter, Maximum Severity, Time Point, and Study Group – Hemoglobin, Safety Population

Time Point	Study Group	N	None		Mild / Grade 1		Moderate/ Grade 2		Severe/ Grade 3		Missing		Not Applicable	
			n	%	n	%	n	%	n	%	n	%	n	%
Screening	M2SR	x	x	xx	x	xx	x	xx	x	xx	x	xx	NA	NA
	Placebo	x	x	xx	x	xx	x	xx	x	xx	x	xx	NA	NA
Day 8	M2SR	x	x	xx	x	xx	x	xx	x	xx	x	xx	NA	NA
	Placebo	x	x	xx	x	xx	x	xx	x	xx	x	xx	NA	NA
Day 22 ^a	M2SR	x	x	xx	x	xx	x	xx	x	xx	x	xx	x	x
	Placebo	x	x	xx	x	xx	x	xx	x	xx	x	xx	x	x
Day 57 ^b	M2SR	x	x	xx	x	xx	x	xx	x	xx	x	xx	x	x
	Placebo	x	x	xx	x	xx	x	xx	x	xx	x	xx	x	x
Max Severity Post Baseline	M2SR	x	x	xx	x	xx	x	xx	x	xx	x	xx	NA	NA
	Placebo	x	x	xx	x	xx	x	xx	x	xx	x	xx	NA	NA

Note: The “Max Post Baseline” rows indicate the maximum severity experienced by each subject at any time point post baseline, including unscheduled assessments.

N = Number of subjects in the Safety Population

^a Any subject with either a drop of > 0.5 g/dL or results less than the lower limit of normal (based on age and gender) at Day 8 will have hemoglobin re-drawn at Day 22

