14.3.5 Displays of Laboratory Results

Figure 56: Laboratory Results by Scheduled Visits: Mean Changes from Baseline by Laboratory Parameter and Study Group – Alanine Aminotransferase

[Implementation Note: An example figure is shown below. Change from baseline will be displayed for each group following the first vaccination (Day 8) in a single panel.]

Figures with similar format:

Figure 57: Laboratory Results by Scheduled Visits: Mean Changes from Baseline by Laboratory Parameter and Study Group – Aspartate Aminotransferase

Figure 58: Laboratory Results by Scheduled Visits: Mean Changes from Baseline by Laboratory Parameter and Study Group – Creatinine

Figure 59: Laboratory Results by Scheduled Visits: Mean Changes from Baseline by Laboratory Parameter and Study Group – Hemoglobin

Figure 60: Laboratory Results by Scheduled Visits: Mean Changes from Baseline by Laboratory Parameter and Study Group – White Blood Cells

Figure 61: Laboratory Results by Scheduled Visits: Mean Changes from Baseline by Laboratory Parameter and Study Group – Platelets

Figure 62: Laboratory Results by Scheduled Visits: Mean Changes from Baseline by Laboratory Parameter and Study Group – Prothrombin Time

Figure 63: Laboratory Results by Scheduled Visits: Mean Changes from Baseline by Laboratory Parameter and Study Group – Activated Partial Thromboplastin Time

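### Hemoglobin falls are summarised without selection only at Day 8: no table counts falls of 0.5 g/dL or more, and the all-subject Day 113 value has no by-visit summary

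*SAP*

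**What the plan says.** SAP 12 gives as one of two reasons for the pause: "Consistent drops in HGB post first vaccination had been noted among the subjects enrolled in 2018". SAP 4.3 reports that the protocol was then amended on iron screening, blood volume and specimen collection.

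- **Who is tested, and when.** Hemoglobin is measured in everyone at screening and Day 8. At Day 22 it is repeated only after a trigger: a value below the lower limit of normal (LLN), or, in SAP 9.6, "subjects who experience a drop of ≥ 0.5 g/dL between screening and Day 8, will have HGB re-drawn at Day 22". It is repeated at Day 57 if still low or if the Day 22 draw was missed. Protocol 9.1 adds "HGB and Ferritin level will be drawn at Day 113", and SAP 9.6 makes that draw universal: "HGB and Ferritin will be drawn for all subjects at Day 113 (approximately 22 days post QIV vaccination".
- **How it is graded.** SAP Table 10 grades absolute values. Grade 1 is 9.5-10.4 g/dL in the row "HgB g/dL 9-12 years of age" and for females 13 and over, and 10.0-10.9 for males 13 and over. Creatinine (Table 11) also has a criterion relative to the subject's baseline; hemoglobin has none.
- **What is displayed.** Tables 60 and 61 have rows for Screening, Days 8, 22 and 57, and maximum severity. Table 66 has hemoglobin rows for Days 8, 22 and 57 and the maximum. Table 67 gives change from screening by arm. For Figures 56-63: "Change from baseline will be displayed for each group following the first vaccination (Day 8) in a single panel".
- **Baseline.** SAP 9.6: "Clinical laboratory evaluations assessed on Day 1 prior to the first study vaccination will be considered as baseline".
- **Trigger in the table footnotes.** "Any subject with either a drop of > 0.5 g/dL or results less than the lower limit of normal".

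**The concern.** Safety is the only primary objective, and hemoglobin is the laboratory signal that changed this trial. The open question is whether M2SR contributed to the falls or whether blood sampling explains them. The randomised placebo arm is the means of answering it.

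After Day 8, the planned by-arm summaries either use grades that a moderate fall does not reach, or describe subjects selected on a post-randomisation outcome. The one later value scheduled for every subject is not tabulated by visit. A persistent or late difference between arms could then be missed in the study report, or be misread from the Day 22 and Day 57 rows.

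**Working it through.** The plan states no design figure on this point, so there is none to reproduce. The documents give no hemoglobin mean or SD. Steps 2, 3, 4 and 6 therefore rest on assumed values, given as ranges where possible.

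**1. Fall needed to be graded.** Inputs: entry minimum 11.5 g/dL (Protocol 5.1, criterion 12) and the Grade 1 upper bounds in SAP Table 10. Required fall = starting value - upper bound.

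| Start (g/dL) | Age 9-12, females 13+ (10.4) | Males 13+ (10.9) |
|---|---|---|
| 11.5 | 1.1 | 0.6 |
| 13.0 | 2.6 | 2.1 |

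A fall of exactly 0.5 leaves at least 11.5 - 0.5 = 11.0, above both bounds. Under the current entry rule it is never graded.

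**2. Share of such falls that are graded.** Assumptions: mean 13 g/dL, between-subject SD 0.9, within-subject SD 0.3-0.5, true fall 0.4. Simulation gives 46-49% of subjects with a fall of 0.5 or more. Of these, 0.2-1.2% are graded at the 10.4 bound and 3-6% at 10.9. A lower assumed mean raises these shares.

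**3. Selection at Day 22.** Let s be the within-subject SD, with independent errors, and use the fall criterion alone. The observed Day 8 change has SD s√2. With no true change, P(selected) = Φ(-z), where z = 0.5/(s√2). The selected subset's mean Day 22 change is -½·s√2·φ(z)/Φ(-z), because the screening error is shared.

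- s = 0.3: z = 1.18, P = 0.12, mean change -0.35.
- s = 0.5: z = 0.71, P = 0.24, mean change -0.46.

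So 12-24% are selected by noise and still look 0.35-0.46 g/dL down at Day 22.

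Now suppose a persistent true fall of 0.5 in the M2SR arm only. Then P = 0.50 in that arm and the subset mean is -0.5 - ½·s√2·(0.399/0.5), which is -0.67 to -0.78. The between-arm difference within the subset is about -0.32 (for s = 0.3, -0.669 + 0.354), against a true -0.5. It rests on about 12.5 versus 3-6 subjects of 25 per arm.

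**4. What Day 113 rows would give.** 95% CI half-width for the difference in mean change = t × SD × √(2/n), with assumed SD of change 0.5-0.8 g/dL:

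- n = 25 per arm: 2.01 × SD × 0.283 = 0.28-0.45.
- n = 22: 0.30-0.49.
- n = 15, if only the 31 subjects enrolled after the pause have the value: 0.37-0.60.

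For a difference in proportions at n = 25, the widest Wald half-width is 1.96 × √(2 × 0.25/25) = 0.28.

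**5. Blood drawn before the Day 113 sample.** Protocol Table 2 gives a cumulative 146 mL through Day 92, including both 4 mL redraws. Without redraws it is 146 - 8 = 138 mL. With both redraws and the 16 mL PBMC sample stopped at Day 92 it is 146 - 16 = 130 mL. Before the Day 8 draw it is 14 + 22 = 36 mL for everyone.

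**6. Trigger wording.** Protocol 7.4.2, 8.2.1 and 9.1, SAP 9.6 and the schedule footnotes use 0.5 or more. SAP 4.5.2 and the footnotes to Tables 60, 61, 66 and 67 use more than 0.5. The footnotes to Tables 66 and 67 define N*, the number expected to be tested. If results are reported to 0.1 g/dL, falls of exactly 0.5 make up about 5-9% of subjects under the step 2 assumptions (2-5 of 50).

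**The case against.** A reader might infer that the planned tables do not measure the drops at all, or that grading removes the signal. The documents do not support that. Table 67 gives mean, SD, median and range of change from screening by arm, and at Day 8 every subject is tested after the same scheduled blood volume. Figure 59 plots the Day 8 change. That comparison is randomised and unselected.

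A reader might also infer that Day 113 hemoglobin is discarded. It is not: Listing 15 holds all results, and the maximum-severity rows cover any post-baseline time. But a listing is not a comparison, and the maximum rows use the same absolute grades without showing the visit.

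Other points on that side:

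- **N* already counts triggered subjects.** Roughly so at Day 22, and the not-applicable column of Table 61 is close to its complement. But N* mixes falls with values below LLN, carries the disputed trigger wording, and says nothing about Day 113.
- **Baseline is defined elsewhere.** This stands. SAP 3.3 uses the last value before first vaccination, which for these labs is screening, and Table 67 is headed accordingly. The Day 1 sentence in SAP 9.6 is a wording slip.
- **Table 67 may be damaged in the text available.** Possibly; platelet Day 8 rows are missing too. Its lack of Day 57 rows is therefore not counted here. The Day 113 gap also appears in Tables 60, 61 and 66.
- **Day 113 is not a clean test of M2SR.** This stands. It follows QIV in both arms, and blood volume after Day 8 can depend on a subject's own hemoglobin.
- **The 2018 cohort may differ.** Later draws and the normal-hemoglobin entry rule came with amendment, so some of those 19 subjects may lack Day 113 values, and the 11.5 arithmetic may not describe them.
- **The trial is descriptive.** This stands, so baseline adjustment is optional. SAP Table 41 already plans arm differences with 95% CIs for solicited events, so the format requested here is not foreign to the plan.

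**Conclusion.** The point holds as a gap in the planned displays. The hemoglobin signal is summarised without selection only as change at Day 8. There is no by-arm count of falls of 0.5 g/dL or more, the later by-arm summaries are selected subsets, and the only late value scheduled for all subjects has no by-visit summary.

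The grade arithmetic (1.1 and 0.6 g/dL from the entry minimum) comes straight from the documents and applies to subjects entered under the current rule. The simulated percentages, the Day 22 selection effect and the interval widths depend on assumed means and SDs that the documents do not give; they show direction and rough size only. An interval of about ±0.3 to ±0.5 g/dL at Day 113 would be informative beside a 0.5 g/dL threshold, less so if only about 15 per arm have the value.

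The change should be made. The gap does not invalidate the safety analysis. The trigger mismatch is inconsistent as written.

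**What to change.** - Add Day 113 hemoglobin rows to Tables 60, 61, 66 and 67 and a Day 113 point to Figure 59. Show n, because some subjects enrolled in 2018 may lack the value.
- Add one table by arm for Day 8 and Day 113: number and % with a fall of 0.5 g/dL or more, number and % below LLN, and the M2SR-placebo difference in mean change with 95% CI. Mark it descriptive; adjustment for screening hemoglobin is optional. Footnote that Day 113 follows QIV and that blood volumes after Day 8 may differ between subjects because of the redraw and PBMC-stopping rules.
- Label the Day 22 and Day 57 summaries as a selected subset, not for between-arm comparison.
- Align the baseline sentence in SAP 9.6 with SAP 3.3 and Table 67 (screening).
- Reconcile the two trigger wordings across SAP 4.5.2, the table footnotes, SAP 9.6 and the protocol. Which one applies is for the sponsor to state; N* must follow it. Showing falls of exactly 0.5 separately would let either definition be recovered.

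The cost is SAP wording, a few rows and one extra table. All the draws are already scheduled.

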### **7.4.3. Visit 04, Day 57, Clinic Visit (Window: 56±3 days post first study vaccination)**

- Interim medical history, including an assessment for new medical conditions will be obtained by interview of parent(s)/legal guardian(s) and any changes since the previous clinic visit or contact will be noted.
- Subject or subject's parent(s)/legal guardian(s) will be asked if the subject had any additional blood taken for medical reasons.
- AEs limited to AESIs, NOCMCs, and SAEs will be recorded on the appropriate data collection form.
- A targeted physical examination may be performed, if indicated based on review of interim medical history, by a study clinician licensed to make medical diagnoses and listed on the Form FDA 1572 as the site principal investigator or sub-investigator.
- Subject's/parent(s)/legal guardian(s) will be counseled on the avoidance of taking any aspirin or salicylate containing products for 30 days prior to receipt of the first vaccination through 21 days after the last vaccination.
- In the event that the subject attends the visit without a parent/legal guardian, the parent/legal guardian will be called to collect updated medical history, concomitant medications, and will be reminded that the subject is to avoid any aspirin or salicylate containing products for 30 days prior to receipt of the first vaccination through 21 days after the last vaccination.
- A nasal swab for sIgA will be obtained.
- Approximately 6 mL of venous blood will be collected for serum HAI, HA/NA ELISA and neutralization assays.
- Approximately 16 mL of PBMCs will be collected for IFN- $\gamma$  ELISPOT and CFSE dilution/ICS assays.
- Approximately 4 mL of venous blood will be collected if Hgb level at Day 22 has dropped 0.5 g/dL or more from baseline or is < lower limit of normal. If results at Day 57 still meet that criteria ( $\geq 0.5$  g/dL drop from baseline or < lower limit of normal), no further PBMC collection will be done. If results have recovered to within 0.4 g/dL of baseline at Day 57, resume blood collection plan for the rest of the study.

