#### **7.4.5. Visit 06, Day 113, Clinic Visit**

**(Window: 21±2 days post second study vaccination)**

- Interim medical history, including an assessment for new medical conditions will be obtained by interview of parent(s)/legal guardian(s) and any changes since the previous clinic visit or contact will be noted.
- Concomitant medications (limited to aspirin or salicylate containing products) will be recorded on the appropriate data collection form.
- All SAEs will be recorded on the appropriate data collection form.
- A targeted physical examination may be performed, if indicated based on review of interim medical history, by a study clinician licensed to make medical diagnoses and listed on the Form FDA 1572 as the site principal investigator or sub-investigator.
- Subject's/parent(s)/legal guardian(s) will be counseled on the avoidance of taking any aspirin or salicylate containing products for 30 days prior to receipt of the first vaccination through 21 days after the last vaccination.
- In the event that the subject attends the visit without a parent/legal guardian, the parent/legal guardian will be called to collect updated medical history, concomitant medications, and will be reminded that the subject is to avoid any aspirin or salicylate containing products for 30 days prior to receipt of the first vaccination through 21 days after the last vaccination.
- A nasal swab for sIgA will be obtained.
- Approximately 6 mL of venous blood will be collected for serum HAI, HA/NA ELISA and neutralization assays.
- Approximately 16 mL of PBMCs will be collected for IFN- $\gamma$  ELISPOT and CFSE dilution/ICS assays. Note: PBMCs will not be collected if the HgB was consistently low through Day 57.

- Approximately 8 mL of venous blood will be collected for Hgb and Ferritin level. If the ferritin level is < 15 ng/mL and/or the Hgb is less than the lower limits of normal, recommend follow-up with primary care provider for consideration of multivitamins with iron.

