## **8.2. Laboratory Evaluations**

### **8.2.1. Clinical Laboratory Evaluations**

Urine pregnancy tests will be performed locally by site laboratory at the Screening visit and within 24 hours prior to each study vaccination (Day 01 (Visit 01) and Day 92 (Visit 05) on all female adolescents of childbearing potential. Results must be negative and known prior to randomization on Day 1 and administration of each study vaccination to be eligible for participation in this study and receipt of each study vaccination.

- Clinical laboratory parameters to be evaluated at the Screening Visit (Visit 00) and on Day 08 (Visit 02) will include a White Blood Cell Count (WC), HGB, HCT (only at Visit 00), Platelet Count, ALT, AST, Serum Creatinine, Ferritin (at Visit 00), Prothrombin Time (PT) and Activated Partial Thromboplastin Time (aPTT). The results from the clinical safety laboratory parameters collected on Visit 00 will be available and reviewed prior to study

vaccination. Results of the HGB and HCT must be within normal limits, and Ferritin must be  $\geq 15$  ng/mL for enrollment. HGB will also be repeated at Day 22 and/or Day 57 if HGB is below the lower limit of normal or  $\geq 0.5$ g/dL below the baseline screening level at the day 8 follow up safety. HGB and Ferritin will be drawn at Day 113.

All other results can be and will serve as a Grade 1 or normal.

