**Table 2: Venipuncture Volumes (mL):**

Study Visit Number	VS00	V01	V02	V03	V04	V05	V06	V07	V08
Study Day post 1st study vaccination	Screen	D01 Dose #1	D08	D22	D57	D92 Dose #2	D 113	D 240	D 366
Study Day post 2 nd study vaccination						D01	D22	D 149	D 275
Clinical Screening and Safety Laboratory Evaluations	14 mL 		14mL 	4mL 	4mL 		8mL 		
Serum for HAI, HA/NA ELISA, Neutralization Assays		6 mL	6 mL	6 mL	6 mL	6 mL	6 mL		
Nasal Swab sIgA		X	X	X	X	X	X		
PBMC for IFN- $\gamma$ ELISPOT CFSE Dilution/ICS Assays		16 mL	16 mL	16 mL	16 mL	16 mL	16 mL		
Total (mL)	14 mL	22mL 	36 mL 	26mL 	26mL 	22mL 	30mL 	0	0
Cumulative Total (mL)	14 mL	36 mL	72 mL	98 mL	124 mL	146 mL	176 mL	176 mL	176 mL

 Verify that for pediatric patients, no more than 5 mL/kg may be drawn for research purposes in a single day, and no more than 9.5 mL/kg may be drawn over any eight-week period. (NIH blood draw policy) or institutional policy is followed.

 Includes HCT.

 Includes WBC, Hgb, Platelet Count, ALT, AST, Serum Creatinine, PT, and aPTT

Includes Ferritin Level.

Includes Hgb; Draw if Hgb drops  $\geq 0.5$  g/dL or < lower limits of normal at previous visit.

Includes Hgb..

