4.3. Selection of Study Population

The study population for this clinical trial is 50 male and non-pregnant female children and adolescents between the ages of 9 and 17 who are in good health and meet all eligibility criteria. Specific eligibility criteria can be found in the protocol sections 5.1 (Subject Inclusion Criteria) and 5.2 (Subject Exclusion Criteria). The subjects are recruited from the general population at the participating Vaccine Trial and Evaluation Unit (VTEU) site, Saint Louis University (SLU), which has substantial experience conducting influenza vaccine studies.

Following review of laboratory results for subjects enrolled through August 2018, it was identified that a significant portion had a drop in hemoglobin during the study. The protocol was amended to include screening for pre-existing iron deficiency anemia with ferritin and requiring both normal ferritin and HgB results for enrollment, to reduce the amount of blood collected overall, and to add a contingency regarding specimen collection. Subjects will be monitored after entry in the trial for drops in hemoglobin levels indicating anemia. If HgB levels are consistently low through the visit at approximately Day 57, the subject will no longer have PBMC samples collected at subsequent visits.

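### The hemoglobin grade tables and figure shell omit Day 113, the only draw after Day 8 scheduled for every child, although SAP 9.6 calls for results by study day

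*SAP*

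**What the plan says.** **Draws.** SAP 9.6 states that "HGB and Ferritin will be drawn for all subjects at Day 113". Protocol 8.2.1 agrees ("HGB and Ferritin will be drawn at Day 113"), and the Protocol 7.4.5 visit list sets no condition: "Approximately 8 mL of venous blood will be collected for Hgb and Ferritin level". Hemoglobin at Day 22 and Day 57 is conditional. Day 22 is for children who by Day 8 have fallen 0.5 g/dL or more or are below the lower limit of normal. Day 57 is for those still low at Day 22 or not drawn then.

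**Summaries.** The SAP 9.6 text promises severity by study day and group, change from baseline by study day for each parameter (Tables 59 and 67), and abnormal results by visit and arm (Tables 58 and 66). It also plans listings of graded results: "Subject visits with abnormal laboratory results, Grade 1 severity or higher, will be presented in" Tables 52 and 53. Listing 15 holds every hematology result.

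**Ferritin.** SAP 9.6 says "Ferritin results taken at Day 57 will be used for clinical decision making only", so those values are listed but neither graded nor summarized.

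**Background.** On reviewing children enrolled through August 2018, SAP 4.3 reports that "it was identified that a significant portion had a drop in hemoglobin during the study". SAP 12 gives the hemoglobin drops as one of two reasons for the November 2018 pause, after which later hemoglobin draws were added.

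**The concern.** Hemoglobin is a known safety signal in this pediatric trial, and the protocol was changed so that recovery could be followed. Day 113 is the only scheduled time after Day 8 at which every child is measured, and it comes at the end of blood collection. If programmers follow the grade and figure shells, the by-arm picture after Day 8 consists of two conditional visits and a worst-grade row.

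The conditional rows show how children who had already fallen, or who missed a draw, did next. A child who passes Day 8 and falls later is next measured at Day 113 and has no row there. The worst-grade row is cumulative, so it cannot show a return to baseline. The protocol judges recovery by change rather than grade: "If results have recovered to within 0.4 g/dL of baseline at Day 57" is its rule for resuming the blood collection plan.

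**Working it through.** **1. Shells against draws**

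| SAP display | Content | Hemoglobin time points in the shell |
|---|---|---|
| Tables 60, 61 | Grade by arm | Screening, Day 8, Day 22, Day 57, worst grade after baseline |
| Table 66 | Grade by arm, treatment-related results only | Day 8, Day 22, Day 57, worst grade after baseline |
| Table 67 | Value and change from screening by arm | Screening, Day 8, Day 22 as read; rows missing |
| Figure 59 | Change from baseline by arm | Day 8, by its similar-format note to Figure 56 |
| Listing 15 | Every result, child by child | All |

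A Day 113 result enters the worst-grade row only if it is graded, and in Table 66 only if it is also judged related.

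Table 67 is not evidence either way. It has a Day 57 footnote but no Day 57 row, and its platelet block has no Day 8 row although platelets are drawn then. Its eligibility note covers only Day 22 and Day 57, but an unconditional draw would need no such note.

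**2. Blood volume (Protocol Table 2)**

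- Reproducing the stated total: 14 + 22 + 36 + 26 + 26 + 22 + 30 = 176 mL, which matches.
- Drawn before the Day 8 visit: 14 + 22 = 36 mL.
- Drawn from the Day 8 visit until just before Day 113, with no conditional 4 mL draws: 36 + 22 + 22 + 22 = 102 mL.
- Total before Day 113: 36 + 102 = 138 mL, and 102/138 = 74%.
- At the 34 kg entry minimum: 102/34 = 3.0 mL/kg. The protocol's eight-week limit of 9.5 mL/kg is 323 mL at that weight, so this is within limits.
- With both conditional draws: 110 mL and 146 mL.

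For a child with no trigger, the Day 8 hemoglobin therefore follows about a quarter of the blood taken before Day 113.

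**3. Falls that carry no grade**

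The entry minimum is 11.5 g/dL (Protocol 5.1). Grade 1 starts at 10.4 g/dL for ages 9–12 and for girls of 13 and over (SAP Table 10), so 10.5 is ungraded: 11.5 − 10.5 = 1.0 g/dL, twice the 0.5 g/dL trigger. For boys of 13 and over, Grade 1 starts at 10.9, so the ungraded fall is 11.5 − 11.0 = 0.5 g/dL. A child entering higher can fall further without a grade.

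**4. Threshold**

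The protocol, SAP 9.6 and the SAP Table 2 footnote use a fall of at least 0.5 g/dL. SAP 4.5.2 and the footnotes of Tables 60, 61, 66 and 67 use more than 0.5. Hemoglobin is graded to one decimal, so a fall of exactly 0.5 can occur. Such a child is due a redraw but would be left out of the expected-for-test count in Tables 66 and 67.

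**5. Ferritin**

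The protocol schedule has ferritin at screening and Day 113, and SAP Table 2 has it at Day 113 only. The Day 57 draw is a conditional 4 mL for hemoglobin. No scheduled result matches the SAP 9.6 sentence.

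**6. What a Day 113 row could show**

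There would be 25 children per arm if all 50 have the draw. If only the 31 planned for 2019 do (50 − 19), there would be about 15–16 per arm. With no falls of 0.5 g/dL or more, the Clopper–Pearson upper 95% limit is 1 − 0.025^(1/n): 13.7% for n = 25, 20.6% for n = 16 and 21.8% for n = 15.

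**The case against.** A reader might infer that the plan nowhere shows Day 113 hemoglobin values or change by arm. The documents do not support that. Tables 60, 61 and 66 are grade tables and show no values at any visit. Values and change belong in Table 67, which has visibly lost rows where later hemoglobin visits would sit. The SAP 9.6 text, by study day for each parameter, covers Day 113 on its face. The Figure 59 limit is also inferred: the Day 8 note sits under the ALT figure, a test scheduled only at screening and Day 8.

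The consequence is limited too. The planned laboratory safety variable is at about 7 days, no primary outcome names laboratory values, and the study tests no hypothesis. Day 113 values are in Listing 15 with study group, graded ones are listed, and worst grade is shown by arm. The 2018 children may not have had the draw.

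All of this stands, and it narrows the point to a mismatch between text and shells. It does not remove it. Tables 60, 61 and 66 are legible and stop at Day 57, against text that promises results by study day or visit. A listing is not a by-arm summary. The only sentence keeping results out of the summaries concerns ferritin, not hemoglobin. Its Day 57 is probably a slip for Day 113, but it is wrong as written. Summarizing ferritin by arm is a preference, not a correction.

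**Conclusion.** The shells should be brought into line with SAP 9.6. As they stand, the grade tables and the figure format give no by-arm view of hemoglobin at the one later visit scheduled for every child. What they show after Day 8 comes from a selected group, plus a row that cannot show recovery or ungraded falls. For a child with no trigger, 74% of the blood drawn before Day 113 is taken from the Day 8 visit onward. Ungraded falls can reach 1.0 g/dL even from the entry minimum.

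This rests on three assumptions: that Figure 59 follows the Figure 56 format, that Tables 60, 61 and 66 are complete as read, and that the Day 113 draw was made. The documents do not date the amendment against the 2018 children's visits, so the third is uncertain for those 19.

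A reader might also hope that a Day 113 comparison would separate a vaccine effect on hemoglobin. It would not, because Day 113 follows QIV and the conditional stop of PBMC draws. The display is descriptive, and no immunogenicity conclusion changes.

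**What to change.** 1. Add Day 113 hemoglobin rows by arm to Tables 60, 61 and 66.
2. Make sure Table 67 and Figure 59 include Day 113 change from screening, and that Table 67 has the Day 57 row its footnote describes.
3. Add, by arm at Day 113, n (%) with a fall of at least 0.5 g/dL, with an exact 95% CI (the SAP's Blaker method will serve).
4. Replace more than 0.5 with at least 0.5 in the shell footnotes and SAP 4.5.2.
5. Correct the ferritin sentence in SAP 9.6 to the scheduled draws, screening and Day 113, and state whether they are summarized. A by-arm ferritin summary is optional.
6. Footnote that Day 113 follows QIV and the conditional stop of PBMC draws, and that 2018 enrollees may lack the draw, so n may be about 15–16 per arm.

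The cost is a few table rows, one figure time point and some corrected wording. No new visit, sample or test is needed.
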